6.1 Primary outcome

Comparative analysis of pre-operative, post-operative, neurological status, and questionnaires

6.2 Secondary outcome

Descriptive data analysis of clinical parameters will be performed. Confidence intervals for relevant treatment effects are calculated using univariate and multi-variate statistical tests.

Patients' data will be compared to historical cohorts and equivalence, or superiority of care will be described.

Further analysis will be performed as comparative effectiveness research (CER) as described above. When applicable cohorts will be matched in a case-control mode.

7. Documentation, Data Management, Archiving

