In addition to the oncological outcome, the neurological outcome is also very important. Depending on the localization of the tumor, its form and compression of intra-spinal structures such as the spinal cord or nerve roots many patients develop neurological deficits. Besides GTR the other goal of resection is the neurological recovery of these patients. Previous reports show that the time point of surgery is important in order to achieve full recovery (Schwake et al., 2018). However, most of the data is derived from retrospective case series. One of the aims of this registry is to prove this hypothesis. These neurological deficits are, as mentioned above, related to the localization of the tumor within the spine, Tumors in the cervical spine would cause mainly gait ataxia, spasticity, and weakness in the upper extremities while tumors in the lumbar spine would lead to deficits in the lower extremities in combination to disturbances of bladder, bowel, and sexual functions. These functions should be evaluated and monitored, before and after treatment.

Other concerns are safety requirements in order to prevent peri-operative complications. For example, the role of intra-operative neurophysiological monitoring. Some authors recommend the utilization intra operative monitoring, however, the evidence level is very low (Jesse et al., 2022; Thakur et al., 2021). Other open questions are for example the utility of microscope, methods for dura closure and thrombosis prevention.

On the other hand, some tumors can be treated with irradiation, some studies showed efficacy of this method mainly in the case of Schwannomas and meningiomas. In case of residual tumor or tumor progression irradiation can be also performed to prevent further growth (Chang & Lee, 2013).

Lastly, in comparison to the methods mentioned above, a wait-and-see approach can be used for asymptomatic patients or those with mild symptoms. In this case, clinical and imaging examinations are performed at regular intervals to check the neurological status and the tumor. This can also be done for longer periods of time because of the benign nature of these tumors with the slow growth. in case of new neurological deficits or progression surgical treatment should be advocated. Overall, it is not certain at what point therapy is indicated, especially in asymptomatic patients. Because many of these tumors are discovered by coincidence during imaging, which was performed due to other symptoms.

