2.3 Methodology

All patients treated in one of the study centers are recorded in a databank (Redcap, see below), which includes information about admission, symptoms, other diseases, treatment, quality indicators and questionnaires regarding quality of life and functionality. Data should be recorded in an anonymized in each center (see below).

For the analysis the CRF includes information about admission, surgery, discharge, and 3 months (90 days) after surgery. In addition, patients should fill out questionnaires on quality of life (EQ-D5) and functionality (ODI or NDI). Later, yearly visits can be completed to have long term results in the future regarding progression free survival (PFS) and overall survival (OS). The CRF is attached to this document.

Univariate and multivariate statistics would be applied to prove which variables might lead to a favorable or unfavorable outcome.

A minimum number of one hundred (N=100) inclusions seems to be adequate in order to perform reasonable analysis. In the event of nonsufficient recruitment, results and further recruitment would be discussed two years after initiation of the study, and annually thereafter.

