2.4.5. List of possible adverse events

Cerebrospinal Fluid (CSF) Leak:

- **Incidence:** Approximately (aprox. 1-4 %)

Details: A study involving 398 patients reported a CSF leak-related complication rate of 4.27%. The use of 6-0 Prolene sutures for dural closure was associated with a lower leak rate compared to 5-0 silk sutures.

Neurological Deficits:

- **Incidence:** Weakness (aprox. 5-20%), new sensory deficits (aprox. 4-16.7%)

Details: In a cohort of 135 patients undergoing spinal tumor resection, postoperative complications included weakness in 20% and new sensory deficits in 16.7% of patients.

Infections:

- **Incidence:** Superficial wound infection (aprox. 1.9%)

Details: Among 52 patients treated with a microscopic keyhole approach for spinal intradural extramedullary tumors, 1.9% experienced a superficial wound infection.

Bowel and Bladder Dysfunction:

- **Incidence:** aprox. 3.7%

Details: Urinary and renal complications were observed in 3.7% of patients after spinal cord tumor surgery.

Spinal Deformities:

Details: Extensive surgical procedures, especially those involving significant bone removal, may lead

to postoperative spinal deformities, necessitating further corrective measures.

General Surgical Complications:

Details: As with any major surgical procedure, there are inherent risks of complications such as bleeding, infection, and adverse reactions to anesthesia

Further adverse events are listed in the CRF.

3. Study Sites and Study Population

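### Section 6.2 promises to describe equivalence or superiority of care from a comparison with historical cohorts, which cannot separate care from case mix

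*Protocol*

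**What the plan says.** Section 6.2 (Secondary outcome) opens with descriptive analysis and then states: "Confidence intervals for relevant treatment effects are calculated using univariate and multi-variate statistical tests". Next comes the sentence at issue, which says of the patients that their "data will be compared to historical cohorts and equivalence, or superiority of care will be described". The following paragraph turns to comparative effectiveness research and ends: "When applicable cohorts will be matched in a case-control mode". It gives no matching variables and does not say whether the historical cohorts are among those to be matched.

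Three other places bear on the point.
- Section 3.2.1 admits adults with any intraspinal extramedullary tumour, without limits on histology or baseline deficit.
- Section 2.3 (Aims) sets preoperative McCormick 1-2 against 3-5 as a comparison of interest for outcome.
- Section 2.4.5 prints rates from elsewhere: "Weakness (aprox. 5-20%), new sensory deficits (aprox. 4-16.7"%. The upper figures come from a single series: "In a cohort of 135 patients undergoing spinal tumor resection, postoperative complications included weakness in 20% and new sensory deficits in 16.7% of patients".

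**The concern.** Superiority of care is a causal statement: the same patients would have fared worse under the earlier care. A comparison with patients treated at another time, and perhaps elsewhere, does not show that. If the registry has more patients with mild preoperative deficits, a different mix of meningioma, schwannoma and ependymoma, or a stricter definition of a new deficit, its rates will differ even if care is identical. Equivalence has the same weakness, because similar rates can arise when a real difference in care is offset by an opposite difference in case mix.

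Section 2.2 says the registry exists to set benchmarks for future studies. A benchmark paper that also reports superior care invites readers to credit the participating centres with something the design cannot show.

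**Working it through.** **No plan figure to reproduce.** The only planned number is the sample size: "A minimum number of one hundred (N=100) inclusions seems to be adequate in order to perform reasonable analysis". It comes with no test, alpha, power, effect size or margin. What follows is illustration, with the assumptions marked.

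**Inputs**
- Registry n = 100 (section 2.3, Methodology).
- Historical cohort A: 20% of 135 = 27/135 (section 2.4.5). The protocol does not designate it as a comparator; it serves here as a realistic example.
- Historical cohort B: 7/135 = 5.2%. *Assumed*, to represent the low end of the printed 5-20% range.
- Two-sided 5% test, historical counts taken as observed. *Assumed.*
- Care identical in both series, with the registry's true weakness rate p differing only through case mix. *Assumed.*

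**Step 1: against cohort A.** The largest registry count significantly below 27/135 is 10. At 10/100 the p-value is 0.046 (Fisher) or 0.037 (uncorrected chi-square); at 11/100 it is 0.074 or 0.064. The chance of looking significantly better is therefore P(X ≤ 10), with X ~ Binomial(100, p).

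| True registry rate p | P(looks significantly better than 27/135) |
|---|---|
| 5% | 0.989 |
| 8% | 0.824 |
| 10% | 0.583 |
| 12.5% | 0.281 |
| 15% | 0.099 |
| 20% | 0.006 |

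**Step 2: the same registry against cohort B.** Only 0/100 is significantly below 7/135. At p = 10% that has probability 0.9^100 = 0.00003. To look significantly worse, the registry needs at least 14 events by Fisher (p = 0.022; 13 gives 0.056) or at least 13 by uncorrected chi-square (p = 0.034; 12 gives 0.058). The two tests differ here, so both are shown.

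| True registry rate p | Looks worse, Fisher: P(X ≥ 14) | Looks worse, chi-square: P(X ≥ 13) |
|---|---|---|
| 10% | 0.124 | 0.198 |
| 12.5% | 0.368 | 0.485 |
| 15% | 0.653 | 0.753 |

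**Step 3: case mix written out.** *Assumed* good-outcome rates, the same in both series: 90% for preoperative McCormick 1-2 and 50% for 3-5. Let the registry have 80% mild patients and the historical cohort 50%.
- Registry: 0.8 × 90% + 0.2 × 50% = 82%.
- Historical: 0.5 × 90% + 0.5 × 50% = 70%.

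The 12-point gap contains no difference in care. By normal approximation, the registry of 100 looks significantly better with probability 51%, 56% or 69% for a historical n of 100, 135 or 398, against a nominal 2.5% in that direction. Milder assumptions give less: with rates of 90% and 70% and a mix of 60% against 50% mild, it is about 6%.

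**Step 4: what standardising does.** Reweighting the registry's stratum rates to the historical mix gives 0.5 × 90% + 0.5 × 50% = 70%, equal to the historical rate, and the spurious gap disappears. This works only for factors that are measured and reported in both series.

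**The case against.** The strongest reply is that 6.2 contains no decision rule. It says equivalence or superiority will be described, in a section that begins with descriptive analysis, and it mentions neither crude rates nor a significance test. That is right. A reader might infer a formal verdict on unadjusted rates, but the text does not go that far, and the thresholds above belong to the illustration. What stands is that superiority of care, even when only described, is a conclusion about cause.

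Second, 6.2 mentions multivariate tests and matching, and the matching sentence could be read to include the historical cohorts. The wording is ambiguous. On either reading the matching is conditional, and the multivariate sentence concerns treatment effects in general.

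Other tempting inferences are not supported:
- *That the cohorts can be picked after the results are known because they are unnamed.* Naming cohorts and covariates is commonly left to the SAP, which is not shown, so their absence is no finding. An SAP that named them would still leave the promised conclusion in place.
- *That matching is impossible.* This would follow if the cohorts were published series without patient-level data. The protocol does not say so; they could be the centres' own earlier patients.
- *That the 5-20% spread is known to be case mix.* Section 2.4.5 is a risk listing and does not describe care in those series. For CSF leak it links the rate to suture choice, so differences in care may contribute.
- *That registry patients are fitter because they must be able to consent.* Nothing shows that historical cohorts differed in this respect.
- *That the protocol itself discounts its comparators.* The remark in section 2.1, "However, most of the data is derived from retrospective case series", concerns timing of surgery and recovery.

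**Conclusion.** The point holds as a limited one. Section 6.2 commits the registry to a statement about care that a non-concurrent, non-randomised comparison cannot support, and no safeguard in the protocol is clearly tied to that comparison.

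The illustration shows that the result can turn on case mix and on the cohort used. With identical care and a true 10% weakness rate, the registry looks significantly better than a 27/135 cohort 58% of the time and essentially never better than a 7/135 cohort. These figures rest on an assumed two-sided 5% test, an assumed low-rate cohort and a registry rate set by case mix alone. Under the McCormick-mix assumptions tried, false superiority ranges from about 6% to 69%. The mechanism does not depend on those values; its size does.

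No primary outcome depends on this comparison, so the wording should be changed, but the study's main objectives are not at risk.

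**What to change.** In section 6.2, replace the clause on equivalence or superiority of care with: *Differences from historical cohorts will be reported with 95% CIs as descriptive context; no conclusion about equivalence or superiority of care will be drawn.*

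Add that, where a historical cohort reports its mix of tumour type and preoperative McCormick grade, the registry rate will be standardised to that mix, or patients matched if patient-level data exist. The flow chart already has McCormick grade recorded at admission, and the resection outcome already depends on tumour type, so no new data collection is needed. The historical cohorts, and the outcome compared with each, should be fixed before outcome data are reviewed; the SAP is a suitable place.

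The cost is one sentence in 6.2, a short list of cohorts and a little more analysis. With 100 patients, some strata will be small and the standardised rates less precise. The registry gives up a superiority-of-care claim. No patient's treatment or follow-up changes.

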7.1 Patient Identification List

All patient data will be collected in a pseudonymized form. The pseudonym is given automatically during registration by Redcap.

7.2 Source Data / Source documents

Source data are, within the meaning of the ICH E6 Guideline, all information in original records and certified copies of original records of clinical findings, observations, or other activities in a clinical trial necessary for the reconstruction and evaluation of the trial. Source data will be documented in various source documents (e.g. hospital records, doctor's report, patient' diaries or evaluation checklists, imaging) and then entered into the electronic Case Report Form (eCRF).

7.3 Recording of Data / Case Report Form (CRF)

Data will be recorded electronically using Redcap, an EDC (Electronic Data Capture) system. For the documentation of study data, the investigator will be given access to an electronic CRF (eCRF) for each recruited patient. Only persons authorized to enter data into the eCRF will have access to the EDC system. All users will be trained to use the EDC system and will comply with the instructions in the study-specific user manual. They will have continuous access to the data and reports of study patients at their own study site. The investigator is responsible for ensuring that the study data will be documented correctly, completely and in a timely manner. A study team physician takes on responsibility for the collected data by signing electronically.

7.4 Data Management

For data management, the validated data management system redcap will be used. All entered data will be stored on servers of the University of Münster. The servers are located in a secure data center and behind a firewall in the network of the University of Münster. A backup of the data will be saved on a daily basis and all data changes will be recorded in an audit trail.

All data will be checked for plausibility during initial data entry. Missing or non-plausible data are highlighted by the system right at input at the clinical study site and may be corrected immediately. Thereafter, according to the data validation plan, further data checks will be performed with regard to completeness and plausibility by the study coordinator. In case of non-plausible or missing data, queries will be sent to the study site.

7.5 Archiving

After the end of the trial the originals of all trial specific documents (Trial Master File) including originals of the CRFs will be stored by the sponsor for at least 10 years in accordance with the applicable regulations (GCP-Verordnung §13(10)), EU directive 536/2914 and applicable EU directives on medical devices).

Furthermore, the investigator stores the ISF (Investigator Site File) including copies of the CRFs for the time period given above.

No trial data or documents must be destroyed without prior written agreement between the study coordinator and the investigators or their designee. queries must be resolved by authorized members of the investigator's staff in the respective study site in a timely manner.

After completion of data entry and data processing, the database will be locked and the data will be exported for statistical analysis. The investigator will receive a CD-ROM of the eCRF data for archiving at the clinical study site.

8. Monitoring, Audits and Inspections

8.1 Monitoring

A quality assurance audit may be conducted by the study coordinator or one other assigned person. The quality assurance auditor must be provided access to all medical records, the investigator's study-related files and correspondence, and the informed consent documentation that is relevant to this study.

9. Ethical and Regulatory Requirements

9.1 Declaration of Helsinki and Legal Requirements

The study will be conducted in compliance with the declaration of Helsinki (current version, October 2024), the current legal provisions regarding data protection, and the principles of Good Clinical Practice (GCP).

The present study will not be started in a center before the competent ethics committee has given a favorable opinion and an approval by the relevant competent federal authority has been obtained.

Besides, for each participating study site a favorable opinion of the respective ethics committee is required.

In case of substantial amendments, a new application will be submitted to the ethics committees and/or the competent federal authorities. Changes will not be implemented in a country unless the competent ethics committee has given a favorable opinion and/or the competent authority has granted an approval.

Issues, which always require a favorable opinion of the ethics committee, are for example:

1. Inclusion of additional study sites,
2. Change of the investigator or his deputy,
3. Changes in any documents addressed to study participants or in any study information addressed to potential study participants.

9.2 Patient Information and Informed Consent

Prior to inclusion into the study, the investigator informs each patient and/or the legal guardians about nature, significance, implications, and risks of the study as well as about the patient's right to withdraw from study participation at any time without any resulting detriment.

With respect to data protection, the investigator furthermore informs that pseudonymized health data will be stored electronically and transmitted to various persons/institutions as explicitly described in the patient information and consent forms.

Patients/legal guardians will furthermore be informed that, if relevant for study evaluation, data once collected cannot be erased after withdrawal of informed consent.

Further, they provide the opportunity for clarification of any study issues.

The patient and/or the parents/legal guardians will be given adequate opportunity to decide whether to or not to participate in this study.

The consent form and the data protection statement are incorporated and archived with the investigator files. In the patient's file it will be stated that the patient is participating in this study and that these documents are archived in the investigator files.

If the Patients/legal guardians are unable to write, in exceptional cases, instead of the written consent required, oral consent in the presence of at least one witness, who was also present during the conversation about the study, may be given. The witness may not be anyone working at the study site nor a member of the investigating team. The orally given consent has to be documented in writing, dated and signed by the witness.

In case of any study issue which requires a change of the patient information sheet, patients and/or their parents/legal guardians already included into the study must, if relevant to them, be informed about these issues orally and in writing and their written consent in further study participation must be obtained.

9.3 Financing

External funding is currently not planned. If funding is requested and approved during the course of the study, the Ethics Committee must be notified immediately.

9.4 Adherence to the Protocol

The Investigator must adhere to the protocol as detailed in this document. Dependent on competence, substantial changes to the protocol will require written favorable opinion by the ethics committee and/or written approval by the competent authority prior to implementation. This does not apply for appropriate urgent safety measures taken to protect the subjects against any immediate hazard.

Any deviations from the protocol must be fully documented in the source documentation and recorded and explained in the CRF.

10 Study Registration, Reporting and Publication

10.1 Study registration

The study is registered in a clinical trials database, which is accessible to the public (www.clinicaltrials.gov; NCT04738162). ???

10.2 Publication Policy

After complete data collection and analysis, the study results will be published. Single publications such as lectures, posters or papers principally require the approval of the Principal Investigator. Inquiries by the press or the public regarding study results are only to be answered by the Principal Investigator.

A manuscript is to be prepared by the Principal Investigator or by a designated co-worker after completing statistical analysis. **All contributors** would be considered as co-authors. The co-authors are required either to agree to the manuscript or to indicate any requests for changes within 4 weeks after receiving the draft of the manuscript to the lead author. Should they fail to meet this requirement agreement will be assumed.

11. Supplements:

11.1 EQ-5D-5L Questionnaire (© 2009 EuroQol Group EQ-5D™ is a trademark of the EuroQol Group)

MOBILITY

I have no problems in walking about

I have slight problems in walking about

I have moderate problems in walking about

I have severe problems in walking about

I am unable to walk about

SELF-CARE

I have no problems washing or dressing myself

I have slight problems washing or dressing myself

I have moderate problems washing or dressing myself

I have severe problems washing or dressing myself

I am unable to wash or dress myself

USUAL ACTIVITIES (e.g. work, study, housework, family or leisure activities)

I have no pain or discomfort

I have slight pain or discomfort

I have moderate pain or discomfort

I have severe pain or discomfort

I have extreme pain or discomfort

PAIN / DISCOMFORT

I have no pain or discomfort

I have slight pain or discomfort

I have moderate pain or discomfort

I have severe pain or discomfort

I have extreme pain or discomfort

ANXIETY / DEPRESSION

[figure not shown]
I am not anxious or depressed

I am slightly anxious or depressed

I am moderately anxious or depressed

I am severely anxious or depressed

I am extremely anxious or depressed

We would like to know how good or bad your health is TODAY.

- This scale is numbered from 0 to 100.
- 100 means the best health you can imagine. 0 means the worst health you can imagine.
- Mark an X on the scale to indicate how your health is TODAY.
- Now, please write the number you marked on the scale in the box below.

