	
Primary Outcome
 
 • Quality of life based on the questionnaire (EQ-D5) • Extent of tumor resection (see CRF): 
 according to surgeon: 
 1. Meningioma: Simpson grade 1 and 2 2. Schwannoma: complete resection, including nerve root 3. Cauda ependymoma: complete resection, including filum terminale according to postoperative MRI, 3 months after surgery 4. Other: surgeon's decision • Neurological status (McCormick Score) (see CRF), 3 months after surgery
Outcome(s)	
Secondary Outcome
 
Imaging: preoperative and postoperative MRI (3 months) according CRF
 
 • Volumetry • Spinal canal occupancy ratio in % 
Further patient reported outcomes:
 
 • Functionality: Neck disability index (NDI) for tumors in the cervical spine, Oswestry disability index (ODI) for tumors in the thoracic and lumbar spine (see CRF) • Local and radicular pain (VAS 1-10) (see CFR) • Neurological status: motor function of each limb, ataxia and gait (mJOA score) (see CRF) • HADS score- based score for anxiety • Questionnaire on bladder, bowl, sexual functionality

	
Quality indicators (QI):
 
Length of hospital stay
 
30- and 90-days readmission
 
Nosocomial infections
 
Blood loss
 
Duration of surgery
 
Progression of the disease or recurrence
 
Other adverse events
 
Mortality
 
Assessment of adverse events according to Common Terminology Criteria for Advers Events (CTCAE) 5.0 and severity according to the Ibañez scale (see CRF)
 
CSF leakage is defined as one, when CSF leakage is identified on imaging of clinically and treatment is required: operative or conservative (Lumbar drain for example)
 
Postoperative kyphosis or deformity is defined, when symptomatic (for example pain) or evident on imaging (for example kyphotic fracture on MRI)

Study design	Registry trial
Statistical analysis	
Primary Outcome
 
Improvement of neurological function, quality of life, and extent of resection
 
Secondary Outcome
 
Descriptive data analysis of clinical parameters is performed. Confidence intervals for relevant treatment effects are calculated using univariate and multi-variate statistical tests

Number of cases	100 patients
Time period	February 2025 until June 2027
Number of centers	N= X

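### Supplement 11.1 prints the pain answers under usual activities, so the EQ-5D-5L form as printed asks about pain twice and never about usual activities

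*Protocol*

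**What the plan says.** The synopsis and Section 2.3 (Aims) list EQ-5D, written there as EQ-D5, first among the primary outcomes: "Quality of life based on the questionnaire (EQ-D5)". Section 6.1 describes the primary analysis as "Comparative analysis of pre-operative, post-operative, neurological status, and questionnaires". The flow chart in Section 1.2 schedules the questionnaire at admission, 3 months and 12 months. Section 2.3 (Methodology) has patients complete it themselves.

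Supplement 11.1 reproduces the EQ-5D-5L. Its third dimension is headed "USUAL ACTIVITIES (e.g. work, study, housework, family or leisure activities)", and the first answer printed below it is "I have no pain or discomfort". The form closes with a rating of overall health today: "This scale is numbered from 0 to 100".

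On the form actually used for data collection, Section 2.3 (Methodology) says "The CRF is attached to this document", and Section 7.3 says "the investigator will be given access to an electronic CRF (eCRF) for each recruited patient". Neither form is part of the text at hand.

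**The concern.** The heading asks about everyday activity, but every answer below it is a grade of pain. A patient given this page cannot report how far usual activities are limited, and is asked about pain twice.

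Three features of the protocol make this more than a blemish in an appendix:

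- **It affects a primary outcome.** Quality-of-life benchmarks are a primary objective, and an EQ-5D-5L profile or index needs a usual-activities level.
- **Pain cannot be assumed to stand in for activity in this population.** Section 2.1 states "Tumors in the cervical spine would cause mainly gait ataxia, spasticity, and weakness in the upper extremities". It does not say whether those deficits come with pain. The inference drawn here is that such deficits can restrict activity without it.
- **The loss would be hard to detect and could not be repaired.** Section 7.4 relies on checks for completeness and plausibility, and a pain level stored in the usual-activities field would pass both. The admission questionnaire precedes surgery, so a missing preoperative answer cannot be collected later. The synopsis gives February 2025 as the start of the study period.

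**Working it through.** The protocol gives no figure to reproduce here. The check is a line-by-line comparison of Supplement 11.1, followed by simple arithmetic on what would follow if that page were used.

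**Step 1. Headings against answers**

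| Heading in 11.1 | Subject of the five answers | Match |
|---|---|---|
| Mobility | walking | yes |
| Self-care | washing and dressing | yes |
| Usual activities | pain or discomfort | **no** |
| Pain / discomfort | pain or discomfort | yes |
| Anxiety / depression | anxiety or depression | yes |

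There are 5 × 5 = 25 answer lines but only 20 distinct answers. All five lines under usual activities repeat the pain lines word for word. A correct form describes 5^5 = 3125 health states. The printed one describes 5^4 = 625 if a patient marks the same level in both pain blocks.

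**Step 2. Could this be a fault of text extraction?** Each of the two headings is followed, in order, by a complete block of five lines. The only missing figure in the questionnaire is under anxiety / depression. For extraction to be the cause, five lines would have had to be replaced in sequence. That is unlikely, though it cannot be strictly excluded.

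**Step 3. Extent, if the printed form is used**

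- Entries affected: 1 of 6 (five items plus the 0-100 scale).
- Answers affected with 100 patients, all followed up: 100 × 2 visits = 200 (admission and 3 months), or 100 × 3 = 300 with 12 months. Section 2.3 (Methodology) calls 100 a minimum, so these counts are not upper limits.

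**Step 4. Effect on a summary score.** The protocol names no value set. Assume an unweighted sum of the five levels, where higher is worse. It runs from 5 to 25, a range of 20.

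- Pain supplies 2 of 5 items instead of 1 of 5.
- Error for one patient = level marked in the first pain block − true usual-activities level, which lies between −4 and +4. One point is 1/20 = 5% of the range, and the extreme is 4/20 = 20%.
- If both pain blocks are answered alike, this error equals pain level − usual-activities level, and it is zero when those two levels agree.
- Under the same condition, error in mean pre/post change = mean pain change − mean usual-activities change.

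Illustration with assumed mean changes (negative means improvement):

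| Pain | Usual activities | Error | Effect on improvement |
|---|---|---|---|
| −0.5 | −1.0 | +0.5 | understated |
| −1.0 | −1.0 | 0 | none |
| −1.0 | −0.5 | −0.5 | overstated |

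**Step 5. What is not affected.** The other four items, the 0-100 scale, and the VAS, NDI and ODI are unaffected. They do not replace the lost item, however. The NDI has a work item but is used only for cervical tumors. The ODI as printed, used for thoracic and lumbar tumors, has no work item, and its social-life item is worded in terms of pain.

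**The case against.** The strongest reply is that a faulty page has been shown, but not a faulty measurement. Data are collected in REDCap on a form that is not shown. The primary outcome is defined by the name of the instrument, without reference to Supplement 11.1, and the supplement names the instrument and its copyright holder. The intended questionnaire is therefore identifiable, and sites may already use a correct licensed copy. This stands as a limit on the consequences, all of which are conditional. It does not remove the defect: Supplement 11.1 is the only EQ-5D text in the protocol, and Section 9.4 binds investigators to the protocol as written.

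It can also be said that the size is partly constructed. The level sum is not in the protocol, 20% is an arithmetic extreme, and equating the error with pain level minus usual-activities level requires both pain blocks to be answered alike. A patient might read the first block as pain during work or housework and answer it differently. That is fair, so the percentages are illustrations and not estimates. The cap of 4 in 20 points and the share of 2 items in 5 hold whether or not the two blocks are answered alike.

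Finally, a rule for faulty records may seem premature when none is known to exist. It applies only if the check finds some, and an index cannot validly be computed without the usual-activities level.

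**Conclusion.** The concern holds. Supplement 11.1 is wrong as written: none of the five usual-activities answers concerns usual activities, the pain block is printed twice, and no other part of the protocol corrects it. This conclusion rests on the printed text alone and needs no statistical assumption.

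The consequence for the data depends on whether the patient form or eCRF repeats the page, which the protocol does not allow one to judge. If it does, the usual-activities dimension and every profile or index using it are invalid at each scheduled visit. The direction of any bias in pre/post change is not known in advance, and its size could be zero. Because a primary outcome is involved and lost preoperative answers cannot be recovered, this must be corrected, and the forms in use checked promptly.

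**What to change.** 1. In Supplement 11.1, replace the five lines under usual activities with that dimension's answers from the licensed EQ-5D-5L.
2. Before further use, compare the REDCap form and every paper form, at every center, with the licensed version.
3. If any records were taken on a faulty form, flag them and set the usual-activities item and any index value to missing. Keep the other four items and the 0-100 scale.

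The cost is one corrected appendix page and a check of one item on the forms. No additional patients, visits or procedures are needed.
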